	9.1	С	Confidentiality	41
	9.2	S	Source Documents	41
	9.3	D	Data Collection	41
	9.4	R	Record Retention	41
	9.5	S	Safety and Quality Monitoring and Record Availability	41
	9.6	Α	Adverse event (AE) Reporting	42
	9.	6.1	Study Reporting Period of Adverse Events	42
	9.	6.2	Study Reporting Period for Serious Adverse Events	42
	9.	6.3	Notification of Serious Adverse Events	43
	9.7	S	Study Termination	43
1().	PU	BLICATION OF RESEARCH FINDINGS	44
1'	1.	LIS	ST OF ABBREVIATIONS	44
12	2.	RE	FERENCES	45
1:	3.	APF	PENDICES	47

List of Figures

FIGURE 1.1.1.1-1: PULMONARY LPS-INDUCED INFLAMMATION IS INHIBITED BY GLS-1027	15
FIGURE 1.1.1.1-2: PULMONARY LPS-INDUCED INFLAMMATION IS INHIBITED BY GLS-1027	16
FIGURE 1.1.1.2-2: GLS-1027 LOWERS PM2.5 INDUCED LUNG INFLAMMATION AND AIRWAY	
RESISTANCE	18
FIGURE 1.1.1.3-1: SARS-COV CASE-FATALITY RELATIVE TO PROVINCIAL AIR POLLUTION	
INDEX	19
FIGURE 1.2-1: STRUCTURE OF GLS-1027	21
FIGURE 1.2-2: STRUCTURE OF MICROCRYSTALLINE CELLULOSE	22

List of Tables	
TABLE 5.2-1. GLS-1027 AND PLACEBO DRUG PRODUCT VIAL LABELS	27

CLINICAL PROTOCOL SYNOPSIS

Title of study: Safety, Tolerability, Efficacy and Dose Response of GLS-1027 in the Prevention of Severe Pneumonitis caused by SARS-CoV-2 Infection

Number of study participants: 132

Study Phase: II

Study Type: Randomized, double-blind, placebo-controlled

Research Hypothesis: GLS-1027 will be safe, well tolerated and reduce the incidence of treatment failure as characterized by 1) advancing to WHO COVID-19 Classification level ≥6 which includes the need for intubation with mechanical ventilation, initiation of extracorporeal mechanical oxygenation (ECMO), or death, in SARS-CoV-2 infected hospitalized patients, 2) need for institution of salvage therapy 72 hours after study entry with either an IL-6 monoclonal antibody or dexamethasone (≥6 mg/day), 3) withdrawing consent from the study, 4) becoming lost to follow-up, or 5) discontinuation of treatment for any reason other than decrease in renal function or pregnancy.

Primary study objectives and outcome variables:

- Incidence of serious adverse events relative to treatment group
- Incidence of treatment failure within 28 days from enrollment

Exploratory study objectives and outcome variables:

- Assess the number of days requiring ICU care relative to treatment group
- Assess the number of days of mechanical ventilation relative to treatment group
- Assess incidence of WHO COVID-19 Classification levels relative to baseline serum IL-6 level
- Assess incidence of WHO COVID-19 Classification levels relative to baseline serum ferritin level
- Assess incidence of WHO COVID-19 Classification levels relative to baseline CRP
- Assess trough level of GLS-1027 relative to serum creatinine
- Assess the maximal level of Positive End-Expiratory Pressure (PEEP) for subjects who are intubated relative to treatment group.
- Assess the number of days of PEEP > 5 cm H₂O for subjects who are intubated relative to treatment group
- Incidence of progression to WHO COVID-19 Classification level 6, or 7, or 8 (individually)
- Assess SARS-CoV-2 IgM antibody responses relative to treatment group

Group	Ν	Treatment assignment	Study drug dose	Treatment schedule
1	44	Placebo + SOC	0 mg	Daily
2	44	GLS-1027 + SOC	120 mg	Daily
3	44	GLS-1027 + SOC	360 mg	Daily

Table S1: Dosing arms and treatment regimen

Study design:

Phase II randomized, double-blind, placebo-controlled, study to assess 2 different doses of GLS-1027 in the prevention of treatment failure among participants admitted to hospital with PCR confirmed infection with SARS-CoV-2 (WHO classification 3 or 4). The enrollment period will extend to 72 hours from hospital admission. Participants will be randomized at a 1:1:1 ratio to either SOC plus placebo, or SOC plus GLS-1027 at either 120 mg or 360 mg daily. Participants will be administered drug until discharge or death for a maximum treatment period of 28 days. Clinical status will be monitored through 56 days from the initiation of treatment.

Sample Size:

Based early literature reports ^[1], it is anticipated that approximately 50% of subjects hospitalized with PCR-positive SARS-CoV-2 infections (WHO COVID-19 Classification level 3 or 4) will progress to WHO COVID-19 classification level of 6 or greater as defined by one or more of the following: the need for intubation or mechanical ventilation (level 6), the need for ECMO (level 7), or any cause death (level 8). The sample size estimate for this proof of concept is based on Fisher's Exact two-sided test for 2 proportions using NQuery 8 (www.statsols.com).

Although the interim analysis will utilize masked treatment assignments, the O'Brien Fleming group sequential sample size estimation confirms that a single interim look would retain a cumulative exit probability of 70% with a cumulative alpha =0.05 after the final analysis using the target enrollment of 132 (44 per group) to detect a reduction of those reaching the endpoint of treatment failure, which includes advancing to WHO COVID-19 Classification level \geq 6 from 50% (SOC treated) to 25% in either treatment group of SOC plus GLS-1027. Other conditions also qualify a subject as treatment failure include: need for salvage therapy with IL-6 monoclonal antibody; or institution of salvage therapy with dexamethasone (\geq 6 mg/day), withdrawing consent from the study, becoming lost to follow-up, or discontinuation of treatment for any reason other than renal function or pregnancy. This study is not powered to assess statistically significant differences between GLS-1027 doses.

Study assessments:

Adverse events will be monitored and recorded throughout hospitalization from the point of enrollment. Daily assessments of vital signs and clinical laboratory parameters will be reviewed and recorded. Follow-up clinical status will be assessed to Day 56. The first 15 persons enrolled will be included in a pharmacokinetic sub-study assessment to determine elimination of GLS-1027, while trough levels will be monitored throughout the study.

Efficacy will be assessed by evaluating the difference in the proportion of treatment failures by group. Treatment failure will be defined as any of the following:

- 1) progression to WHO COVID-19 classification level of 6 or greater within the 28 days of treatment initiation,
- need for salvage therapy with IL-6 monoclonal antibody; or institution of salvage therapy with dexamethasone (≥ 6 mg/day),
- 3) withdrawing consent from the study,
- 4) becoming lost to follow-up, or
- 5) discontinuation of treatment for any reason other than renal function or pregnancy.

A masked interim analysis will be performed when 22 subjects in each group have been assessed for the primary endpoint of treatment failure. The interim analysis is intended for blinded safety assessment. Unless safety is of concern, the study will not be stopped for futility and enrollment will continue to the targeted sample size of 132.

Study population:

Inclusion criteria for enrollment:

- 1. Age 18 years or older
- 2. Able to provide consent
- 3. Able and willing to comply with study procedures
- 4. Enrollment within 72 hrs of hospitalization with a diagnosis of PCR confirmed SARS-CoV-2
- 5. WHO COVID-19 classification level 3 or 4

Exclusion criteria for enrollment:

- 1. Pregnant or lactating
- 2. SpO2 less than 90% on room air or less than 95% if on supplemental oxygen
- 3. Calculated GFR < 60 (Cockcroft-Gault)

4. Meets hospital COVID-19 treatment algorithm for treatment with dexamethasone at a dose of 6 mg/day for a 10-day course. A single bolus dose of 6 mg of dexamethasone given in the

Emergency Department and continued at a dose of \leq 3.5 mg/day or less is allowed.

- 5. Meets treatment algorithm criteria for treatment with toclizumab or other anti-IL-6 agent
- 6. Treatment with an anti-IL-6 inhibitor, anti-IL-1 inhibitor, anti-TNF monoclonal antibody, or anti-JAK inhibitor (see Appendix A exclusionary period for specific drugs)
- 7. Participation in a COVID-19 clinical trial that includes prescription of a drug with anti-cytokine activity
- 8. Treatment within the past 60 days with a chemotherapeutic agent
- 9. Current treatment with systemic corticosteroids at a dose equivalent of 20 mg/day or greater of prednisone or prednisolone, 16 mg/day or greater of methylprednisolone, or 4 mg/day or greater of dexamethasone
- 10. Diagnosis of leukemia or lymphoma
- 11. WHO COVID-19 classification level of 5 or greater (use of high-flow oxygen, non-mechanical ventilation such as CPAP, mechanical ventilation)

GeneOne Life Science, Inc.

GLS27-005 Clinical Protocol

Table S2: Schedule of Eve	ents	pe	r Sti	udy	Da	y																							-	
Tests and Observations	1	2	3	4	5	6	7	8	9	10	11	12	13	14	15	16	17	18	19	20	21	22	23	24	25	26	27	28	29	56 ^m
Clinical Evaluations																														
Obtain written Informed Consent	Х																													1
Confirm Eligibility Criteria	Х																													
Demographics	Х																													
Medical History	Х																													
Concomitant Medications	Х	Х	Х	Х	Х	Х	Х	Х	Х	Х	Х	Х	Х	Х	Х	Х	Х	Х	Х	Х	Х	Х	Х	Х	Х	Х	Х	Х	Х	Х
Review Medical Record	Х	Х	Х	Х	Х	Х	Х	Х	Х	Х	Х	Х	Х	Х	Х	Х	Х	Х	Х	Х	Х	Х	Х	Х	Х	Х	Х	Х	Х	Х
WHO COVID-19 Classification (Appendix B)	Х	Х	Х	Х	Х	Х	Х	Х	Х	Х	Х	Х	Х	Х	Х	Х	Х	Х	Х	Х	Х	Х	Х	Х	Х	Х	Х	Х	Х	Х
Safety Evaluations																														
Record Adverse Events	Х	Х	Х	Х	Х	Х	Х	Х	Х	Х	Х	Х	Х	Х	Х	Х	Х	Х	Х	Х	Х	Х	Х	Х	Х	Х	Х	Х	Х	Х
Record Vital Signs ^a	Х	Х	Х	Х	Х	Х	Х	Х	Х	Х	Х	Х	Х	Х	Х	Х	Х	Х	Х	Х	Х	Х	Х	Х	Х	Х	Х	Х	Х	Х
Record Hematology ^b	Х	Х	Х	Х	Х	Х	Х							Х							Х							Х		
Record Basic Metabolic Panel, LFTs °	Х	Х	Х	Х	Х	Х	Х							Х							Х							Х		
Record other labs ^d (for days available)	Х	Х	Х	Х	Х	Х	Х	Х	Х	Х	Х	Х	Х	Х	Х	Х	Х	Х	Х	Х	Х	Х	Х	Х	Х	Х	Х	Х	Х	
Record Procalcitonin (baseline value) ^e	Х																													
Record admission CXR	Х																													
Record if care given in ICU setting	х	Х	Х	х	Х	х	Х	Х	Х	х	х	х	х	х	Х	Х	Х	Х	Х	Х	Х	х	х	Х	Х	х	х	х	х	
Record whether nasal O ₂ prescribed and dose level (L/min) ^f	х	х	х	х	х	х	х	х	х	х	х	х	х	х	х	х	х	х	х	х	х	х	х	х	х	х	х	х	х	
Record whether CPAP prescribed and expiratory pressure ^g	х	х	х	х	х	х	х	х	х	х	х	х	х	х	х	х	х	х	Х	Х	Х	х	х	х	х	х	х	х	х	
Record if mechanically ventilated and level of PEEP, % FiO ₂ ^h	х	х	Х	х	х	х	х	х	х	х	х	х	х	х	х	х	х	х	х	Х	Х	х	х	х	х	х	х	х	х	
Record if treated by ECMO	Х	Х	х	х	х	х	Х	Х	Х	х	х	Х	х	х	Х	Х	Х	Х	Х	Х	Х	х	х	Х	Х	х	х	Х	х	
Record admission ECG	Х																													
Study Related Procedures																														
Administer assigned study drug ⁱ	Х	Х	Х	Х	Х	Х	Х	Х	Х	Х	Х	Х	Х	Х	Х	Х	Х	Х	Х	Х	Х	Х	Х	Х	Х	Х	Х	Х	(X)	
Perform urine pregnancy test	Х																													
Perform ECG (12-lead) ^j		Х													Х															
Collect serum for CPK, GGT ^k	Х					l	Х		l			l					l	l				Ī				l		l		
Collect blood for plasma for PK assessment ¹		Х																												
Collect blood for plasma for trough drug measurement (AM blood draw)		х	х	х					х							х							х					х		

GLS27-005

GeneOne Life Science, Inc.

Clinical Protocol

Collect blood for serum (10mL red top,3 tubes)	Х		Х		Х				Х				Х			Х	
Collect blood for PBMCs (10mL ACD; 3 tubes)	Х		Х		Х				Х				Х			Х	
Blood volume for serum, PBMCs	60		60	5	60				60				60			60	

^a Vital signs to be recorded daily to include maximal and minimal: temperature, respiratory rate, heart rate, systolic and diastolic blood pressure

^b Hematology labs to be collected as necessary and recorded: Hemoglobin, hematocrit, platelets, neutrophils, band forms, lymphocytes, eosinophils

^c Basic metabolic panel labs to be collected as necessary and recorded: Sodium, potassium, CO₂ (bicarbonate), creatinine, BUN, glucose, liver function tests (LFTs) that should be recorded include AST, ALT, bilirubin (direct), alkaline phosphatase, LDH, albumin. These labs are performed daily per the hospital COVID algorithm.

^d Other labs to be recorded as available: Ferritin, CRP, IL-6, troponin, D-dimer

^e Procalcitonin: record only initial measurement or within 48 hours of admission and/or SARS-CoV-2 diagnosis (may be performed prior to date of enrollment) ^f Record maximal daily level of O₂ by nasal cannula prescribed, if applicable

⁹ Record maximal daily level of end expiratory pressure delivered by CPAP prescribed, if applicable

^h Record maximal daily level of PEEP and delivered FiO₂ by mechanical ventilation, if applicable

¹ Study drug administration will commence on the day of enrollment if treatment can be administered before 10 pm and then with AM medications thereafter, If, study drug cannot be administered prior to 10 pm on the day of enrollment, then the 1st day of treatment will occur on the day after enrollment.

¹ Perform a 12-lead ECG on the 2nd day of treatment with study drug between 75 and 90 minutes post-administration on day 2; and on day 15 (± 2 days)

^k Serum is collected for CPK and GGT on day 1 and day 7, and weekly thereafter, if values on day 7 are abnormal until return to normal

¹ PK assessment will be performed for the initial 15 subjects enrolled. Blood (5 ml) will be collected for plasma collection at baseline (pre-treatment), and then at 1, 2, 4, and 8 hr. Trough measurements will be obtained as indicated for all study participants

^m The clinical record should be reviewed through to Day 56 as relevant to denote date of discharge, date of death, or clinical status (WHO COVID-19 Classification Level) at Day 56

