8.6 Efficacy Analysis

The primary endpoint is treatment failure which is defined as any subject who achieved WHO level \ge 6 (intubation and mechanical ventilation, requirement for ECMO, or death) within 28 days of initiating treatment or who meet the following reasons for treatment failure:

- Receiving salvage therapy with either an IL-6 monoclonal antibody or for those who are prescribed daily dexamethasone starting 72 hours or later after the 1st dose of study drug within the 28-day primary treatment period.
- Lost to follow-up through hospital transfer, within the 28-day primary treatment period.
- Discontinuation of study drug for any cause prior to discharge will be considered as a treatment failure, except for those for whom study drug was suspended due to a decrease in renal function (creatinine clearance of < 60 mL/min), and those become pregnant during treatment. These subjects will be followed for the primary endpoint for up to 28 days post enrollment, and for up to 56 days for safety.

Subjects who complete 28 days of treatment but remain hospitalized without increase in WHO COVID-19 Classification level to ≥ 6 , will not considered be as treatment failures with respect to the primary endpoint.

The proportion of subjects in each treatment group who reach the study endpoint of treatment failure by 28 days will be compared to placebo using Fisher's Exact 2-sided test of proportions. Additionally, the frequency for each outcome (intubation, ECMO, death) will be determined within each group. The ITT, mITT and PP analysis populations will be used to analyze the primary endpoint.

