Treatment Failure [1]	x (xx.x%)	x (xx.x%)	x (xx.x%)	
Achieved WHO level >=6	x (xx.x%)	x (xx.x%)	x (xx.x%)	
Lost to follow-up	x (xx.x%)	x (xx.x%)	x (xx.x%)	
Withdrawal of informed consent	x (xx.x%)	x (xx.x%)	x (xx.x%)	
Required salvage therapy	x (xx.x%)	x (xx.x%)	x (xx.x%)	
Discontinued study drug prior to discharge	x (xx.x%)	x (xx.x%)	x (xx.x%)	
Had missing assessment of WHO level classification	x (xx.x%)	x (xx.x%)	x (xx.x%)	
p-value [2]	0.xxxx	0.xxxx	, ,	
Maximum WHO Level = 6 (Intubation or Mechanical Ventilation)	x (xx.x%)	x (xx.x%)	x (xx.x%)	
Maximum WHO Level = 7 (Requirement for ECMO)	x (xx.x%)	x (xx.x%)	x (xx.x%)	
Maximum WHO Level = 8 (Death)	x (xx.x%)	x (xx.x%)	x (xx.x%)	

^[1] Subjects who met any of the reasons listed are considered treatment failures. Subjects who failed treatment for multiple reasons are counted once for each reason.

Reference: Listing 16.2.6.1

Programming note: Repeat for Table 14.2.1.2 Analysis of Overall Treatment Failure (mITT Population).

Programming note: Repeat for Table 14.2.1.3 Analysis of Overall Treatment Failure (PP Population).

Programming note: P-values will not be provided for corticosteroid use/non-use subset pages.

^[2] P-value is calculated using a Fisher's exact test and compares the active treatment to placebo. Will only be provided for the 120 mg group if the 360 mg group is significant.

GeneOne Life Science Inc.

Page 1 of 1

Protocol: GLS27-005

Table 14.2.2.1.1

Summary of the Number of Days Requiring ICU Care
(ITT Population)

	GLS-1027	GLS-1027	Placebo
	120 mg	360 mg	(N=XX)
	(N=XX)	(N=XX)	, ,
umber of Days Requiring ICU Care			
n	X	X	Х
Mean (SD)	xx.xx (xx.xxx)	xx.xx (xx.xxx)	xx.xx (xx.xxx)
Median	x.xx	x.xx	x.xx
nearan			xx.x, xx.x

Reference: Listing xxxxx

Programming note: Repeat for Table 14.2.2.1.2 Summary of the Number of Days Requiring ICU Care (PP Population).

Protocol: GLS27-005

Table 14.2.2.2.1

Summary of the Number of Days on Mechanical Ventilation
(ITT Population)

	GLS-1027	GLS-1027	Placebo
	120 mg	360 mg	(N=XX)
	(N=XX)	(N=XX)	, ,
umber of Days on Mechanical Ventilation			
umber of Days on Mechanical Ventilation n	х	x	×
	x xx.xx (xx.xxx)	x xx.xx (xx.xxx)	x xx.xx (xx.xxx)
n			

Reference: Listing 16.2.6.2

Programming note: Repeat for Table 14.2.2.2.2 Summary of the Number of Days on Mechanical Ventilation (PP Population).

Protocol: GLS27-005

Table 14.2.2.3.1 Summary of the Number of Days Requiring Nasal Oxygen (O_2) Administration (ITT Population)

	GLS-1027	GLS-1027	Placebo

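### Two-sided Fisher's exact test, the only planned efficacy test, is valid but conservative; an exact test that contains it gains about 6 points of power with equal arms and 1 to 4 with slightly unequal arms

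*Protocol*

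**What the plan says.** The Sample Size part of the protocol synopsis says "The sample size estimate for this proof of concept is based on Fisher's Exact two-sided test for 2 proportions using NQuery 8"; Protocol 8.2 and SAP section 4 repeat this. The design is described as "using the target enrollment of 132 (44 per group"), to detect a fall in treatment failure "from 50% (SOC treated) to 25% in either treatment group of SOC plus GLS-1027". On power it says that "a single interim look would retain a cumulative exit probability of 70"%, "with a cumulative alpha =0.05 after the final analysis".

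For the primary analysis, Protocol 8.6 and SAP 8.2 both say that the proportion failing in each dose group "will be compared to placebo using Fisher's Exact 2-sided test of proportions". Footnote [2] of SAP Table 14.2.1.1 confirms it: "P-value is calculated using a Fisher's exact test and compares the active treatment to placebo". That footnote and SAP section 4 make the 120 mg comparison conditional on a significant 360 mg result. Protocol 8.6 has no such order.

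No other efficacy test is planned. SAP 8.4 plans no formal testing of the exploratory endpoints, and the corticosteroid subset pages carry no p-values. Neither document gives the attained size of Fisher's test or mentions an unconditional exact test.

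**The concern.** Fisher's test conditions on the total number of failures. Here the arm sizes are set by design but that total is not. The conditional test can use only the few p-values available for each total, so it rejects less often than 5% under the null.

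The efficacy conclusion rests on this one test, and the planned power is only 70%, so a few points matter. Some results just short of the planned effect would be called non-significant although an exact 5% test rejects. Under the SAP's gate, a missed 360 mg result also removes the 120 mg test.

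**Working it through.** **Inputs.** 44 per arm, failure rates 50% v 25%, two-sided alpha 0.05 (protocol synopsis and 8.2). The interim look is masked, for safety, with no efficacy stop, so the final test is taken at 0.05.

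**1. The plan's own 70%.** Normal approximation, unpooled: SE = √[(0.50×0.50 + 0.25×0.75)/44] = 0.0997; 0.25/0.0997 − 1.96 = 0.547; power Φ(0.547) = 70.8%. With one O'Brien-Fleming look at half the information this becomes 70.4% (classic boundary) or 70.6% (Lan-DeMets). The pooled fixed-design version gives 68.4%. So 70% is reproduced by a normal-approximation calculation, not by the Fisher test that the text names.

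**2. Fisher at 44 v 44.** Enumerate all 45 × 45 tables (a, b). Let R(a,b) = 1 if Fisher's two-sided p ≤ 0.05.
- Size(π) = ΣΣ R(a,b)·Bin(a;44,π)·Bin(b;44,π). The maximum over π is 3.06%, at π ≈ 0.36; size is 2.55% at π = 0.50 and 2.65% at π = 0.25. Unused share of alpha: (5 − 3.06)/5 = 39%.
- Power = ΣΣ R(a,b)·Bin(a;44,0.50)·Bin(b;44,0.25) = 61.1%.

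**3. Boschloo at 44 v 44.** Its p-value is the maximum over π of the probability of a table whose Fisher two-sided p is no larger than the one observed. At this sample size it rejects when Fisher's p ≤ 0.0734. Maximum size is 4.78% and power 67.3%. Because the cut-off on Fisher's p is above 0.05, its rejection region contains Fisher's. Barnard and Berger-Boos versions give the same 67.3%.

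Examples at 44 v 44 (Fisher p, Boschloo p): 18 v 9 failures, 0.063 and 0.042; 20 v 11, 0.073 and 0.048.

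Power at other rates, taken as assumptions: 40% v 20%, 44.8% to 53.3%; 35% v 15%, 48.8% to 57.8%; 30% v 10%, 56.1% to 64.9%.

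**4. Other arm sizes** (placebo first, 50% v 25%; gain = difference of the rounded figures):

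| Arms | Fisher power | Boschloo power | Gain (points) |
|---|---|---|---|
| 43 v 43 | 60.8% | 67.4% | 6.6 |
| 44 v 44 | 61.1% | 67.3% | 6.2 |
| 45 v 45 | 62.5% | 68.6% | 6.1 |
| 43 v 44 | 65.1% | 68.0% | 2.9 |
| 44 v 43 | 63.5% | 66.0% | 2.5 |
| 44 v 45 | 66.4% | 69.3% | 2.9 |
| 43 v 45 | 64.1% | 66.1% | 2.0 |
| 45 v 43 | 65.8% | 69.7% | 3.9 |
| 42 v 44 | 63.3% | 64.3% | 1.0 |

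Fisher's maximum size is about 3.0–3.2% with equal arms but 3.8–4.1% in the slightly unequal splits. At 43 v 44 it is 3.9%, leaving (5 − 3.9)/5 = 22% of alpha unused.

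**5. Two doses against one placebo arm, no gate.** With r(a) the chance that one dose is declared different given a placebo failures, family-wise error = Σ Bin(a;44,π)·[1 − (1 − r(a))²]. The maximum is 5.7% with Fisher and 8.7% with Boschloo. With the SAP's gate it is at most the per-comparison size: 3.06% and 4.78%.

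**The case against.** Fisher's test is valid, conventional, prespecified and named consistently in both documents, and this is a phase II proof of concept. That stands: the point concerns efficiency, and no comparison loses error control because of Fisher's test.

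Four stronger readings are tempting, and none is supported.

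- *That about 40% of alpha is always wasted and 6 points are always on offer.* This belongs to equal arms. Protocol 8.3 stratifies randomisation by site, Protocol 3.2 enrols at least 44 per group, and 7.3.2 allows an increase, so exactly equal arms are not assured. In the six splits checked that pair arms of 43 to 45 unequally, the gain at 40% v 20% is only 1.5 to 2.0 points.
- *That the gain is worth 18 patients.* Among equal-arm designs, Fisher reaches 67.5% only at 50 per arm (3 × 6 = 18 more). But Fisher at 44 v 45 already has 66.4%, so the comparison reflects discreteness and does not price the gain.
- *That the planned effect itself would be missed.* It would not: 22/44 v 11/44 has Fisher p = 0.027, and 21 v 11 (0.045), 22 v 12 (0.048) and 20 v 10 (0.042) are also significant. The results that change are somewhat smaller: 18 v 9 is 41% v 20%.
- *That any test called Boschloo's dominates Fisher.* A version that doubles the one-sided p-value does not when the arms differ: 8/44 v 2/45 has Fisher p = 0.0496 but doubled p = 0.056.

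It is also fair that 67% still falls short of the stated 70%. The change recovers part of the gap and does not close it.

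**Conclusion.** The concern holds as a loss of efficiency of moderate size. At the documents' own 44 v 44 and 50% v 25%, replacing Fisher by the exact test that contains it raises power from 61.1% to 67.3% with exact size at most 4.78%. With slightly unequal arms the gain is about 1 to 4 points; it was positive in every split checked.

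This rests on a two-sided 0.05 level at the final analysis, one analysis population (the figures are for the ITT comparison), the SAP's gate, and ordering by Fisher's two-sided p-value. At 44 v 44 the Boschloo result is unchanged at 0.048, an approximate O'Brien-Fleming final level, where Fisher falls to 59.6%. Spare alpha exists only with the gate: under Protocol 8.6 read alone, two ungated Fisher comparisons can already reach 5.7%.

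**What to change.** Before unblinding:

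1. In Protocol 8.6, SAP 8.2 and footnote [2] of SAP Table 14.2.1.1, replace Fisher's test with Boschloo's unconditional exact test at two-sided 0.05. State that tables are ordered by Fisher's two-sided p-value (not a doubled one-sided p-value), that the p-value is maximised over the common failure rate, and that it is computed from the actual arm sizes.
2. Add to Protocol 8.6 the testing order now found only in the SAP: 360 mg first, 120 mg only if 360 mg is significant. Do not change the test without this; ungated, the family-wise error would reach 8.7%.
3. Restate power on the named test: about 67% at 50% v 25% with 44 per arm. Note that slightly unequal arms change this figure.
4. Do not substitute the uncorrected Pearson chi-square. Its 70.1% power looks better, but its exact size reaches 6.0%.

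Cost: wording in both documents, and a short validated program in place of a standard procedure (SAP section 5 specifies SAS 9.4 or higher). The test is less familiar to readers. No patients or data are added, and no result significant under Fisher is lost.

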6. STUDY PROCEDURES AND TREATMENTS

6.1 Procedures by Visit (also see Table S2)

6.1.1 Day 1: Review Study and Eligibility Criteria; Obtain Informed Consent, Enrollment Subjects will be recruited and Study staff will review the protocol with the prospective participant and obtain written informed consent. One copy of the informed consent form (ICF) will be maintained with the investigative team, and the other given to the participant. Study procedures that will be completed include:

- Document review of ICF process and that copy was provided to participant
- Review and record medical history, demographics
- Review concomitant medications
- Record physical exam, height, weight, vital signs from medical record
- Record baseline ECG
- Record COVID-19 PCR result
- Record baseline CBC and Basic Metabolic Profile (BMP), liver function tests (LFTs), CRP, IL-6, troponin, D-dimer, procalcitonin, admission CXR
- Determine and record baseline WHO COVID-19 Classification (Appendix B)
- Record whether participant is prescribed supplemental nasal O_2 and flow rate or O_2 via facemask and Fi O_2
- Perform urine pregnancy test if person is of child-bearing potential
- Collect blood for CPK and GGT
- Alert Pharmacy to enrollment to direct administration of study drug per randomization (if drug administration would occur after 10 pm, then start study drug on Day 2)
- Collect serum and PBMCs as indicated in the Schedule of Events

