6.2.2 Enrollment (Day 1)

Participants who consent to be in the study will be assigned a unique participant identification designation number (PID#). PID#'s consist of a 3 digit site code followed by a 3-digit subject number. Subject numbers are assigned in numerical order of enrollment (i.e., 1st subject is assigned XXX-001, 2nd subject is assigned XXX-002 with XXX a placeholder for the site number). Once assigned, PID numbers cannot be reused for any reason. Information regarding participant's PID# will also be documented on a screening log. Study personnel will alert pharmacy to enrollment for drug administration and review medical record for study related procedures.

Medical History

Investigators should document all significant illnesses that the participant has experienced as Medical History in the last 6 months. Illnesses' first occurring or detected during the study and/or worsening of an existing illness that occurs after the first administration of study drug are documented as AEs on the electronic case report form (eCRF).

Prior and Concomitant medications

Prior treatments, defined as administered up to 4 months prior to the time of enrollment with designation as to whether the drug was prescribed as an outpatient or only since admission, will be recorded in the eCRF as prior medications. Concomitant treatments, defined as continuing or new treatments taken at or after the signing of the informed consent, will be recorded in the eCRF as concomitant medications.

Review and record baseline labs

The medical record will be reviewed and labs from the day of enrollment recorded. Labs and evaluations such as procalcitonin, CXR, D-dimer, troponin will be recorded from the 1st recorded instance in the medical record if not repeated through to the time of or on the day of enrollment.

Determine and record WHO COVID-19 classification level

Determine from the clinical record the WHO COVID-19 classification level (Appendix B) and record. This will be determined and recorded on a daily basis.

Review and record oxygenation status

Document that participant is prescribed nasal O₂ and the flow rate.

If mechanically ventilated, record level of PEEP and %FiO2

Record if CPAP prescribed and expiratory pressure

Record if given ECMO treatment

Contact pharmacy for study drug administration

Contact the investigational pharmacy regarding study recruitment for assignment of randomization code and to dispense study drug to inpatient ward.

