8.4. Analysis of the Exploratory Efficacy Endpoints

PEEP values during intubation will be plotted separately by treatment over time. Assessment of WHO COVID-19 Classification at 28 day relative to treatment group is discussed in Sections 8.1 and 8.2. Shift tables for worst (most extreme) values of serum IL-6 level, serum ferritin level, and CRP relative to baseline will be presented for each WHO COVID-19 Classification level.

The number of days in ICU, requiring mechanical ventilation and of PEEP > 5 cm H₂O will be summarized by treatment using descriptive statistics (sample size, mean, median, SD, minimum, maximum).

The number and percentage of subjects will be summarized by treatment according to their SARS-CoV-2 IgM antibody response. The above exploratory endpoint analyses will be presented for the PP population and individual results will be listed by treatment and study day. No formal statistical analysis is planned.

CONFIDENTIAL Page 12 03DEC2021

The relationship of trough level of GLS-1027 to serum creatinine relative to treatment group will be examined on an adhoc basis and is outside the scope of this document.

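### The first trough and the PK profile are fixed to Day 2 from enrolment, but the first dose may fall on Day 1 or Day 2, so Day 2 samples mix undosed, short-interval and true 24 h values

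*Protocol*

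**What the plan says.** Protocol Sections 6.1.1 and 6.2.2 make the day of enrolment Day 1. Footnote i of Protocol Table S2 gives the dosing rule: "Study drug administration will commence on the day of enrollment if treatment can be administered before 10 pm and then with AM medications thereafter"; otherwise "then the 1st day of treatment will occur on the day after enrollment". Section 6.1.1 confirms that the day count does not move with the dose: "if drug administration would occur after 10 pm, then start study drug on Day 2". The dosing row of Table S2 allows for a late start with a bracketed mark on Day 29.

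The sampling rows make no such allowance.

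- **Trough.** The row reads "Collect blood for plasma for trough drug measurement (AM blood draw") and is marked on Days 2, 3, 4, 9, 16, 23 and 28 (Days 2, 3, 4 and 7 in SAP Table 1). No clock time or interval since the last dose is given.
- **PK.** Section 6.1.2 places the profile on Day 2, with a pre-dose sample and four post-dose samples. Footnote l describes the same profile differently: "Blood (5 ml) will be collected for plasma collection at baseline (pre-treatment), and then at 1, 2, 4, and 8 hr". SAP Listing 16.2.5.3 also labels the first sample pre-treatment.
- **ECG.** Footnote j says "Perform a 12-lead ECG on the 2nd day of treatment with study drug between 75 and 90 minutes post-administration on day 2". Sections 6.1.3 and 6.2.3.5 say Day 2 only.

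Relating trough to creatinine is an exploratory objective (Protocol Section 2.3). SAP Section 8.4 says: "The relationship of trough level of GLS-1027 to serum creatinine relative to treatment group will be examined on an adhoc basis", and places it outside the SAP's scope.

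**The concern.** A trough is interpretable only if the interval since the last dose is roughly constant. Here one label covers patients who have had no drug, patients sampled a full dosing interval after dose 1, and patients first dosed late in the evening and sampled the next morning. If the Day 2 values are pooled as troughs and set against creatinine, differences in sampling interval can be read as differences in elimination.

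The PK sub-study has a related problem. For a Day 1 starter the Day 2 profile follows dose 2 and begins with drug already present. For a Day 2 starter it follows dose 1. With 15 participants randomised 1:1:1, about 15 × 2/3 = 10 are expected on active drug, so mixing the two kinds of curve matters more than it would in a large sample.

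**Working it through.** The plan states no figure on this point to reproduce.

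**Inputs from the documents.** Day 1 is enrolment; the first dose is before 10 pm on Day 1 or else on Day 2; later doses go with AM medications; the half-life is about 7 h (Protocol Section 1.1.2).

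**Assumptions.** The AM draw and AM dose are at 08:00 (range 06:00-10:00), with the draw before that morning's dose. Decay is mono-exponential, absorption is ignored, and doses add by superposition.

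**Consistency check.** Accumulation at 24 h dosing is 1/(1 − 2^(−24/7)) = 1/(1 − 0.093) = 1.10, compatible with the protocol's report of no accumulation.

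**Day 2 sample.** Interval t = (24 − clock hour of first dose) + clock hour of draw. Fraction of the dose-1 level f = 2^(−t/7). Ratio to the 24 h level = 2^((24 − t)/7).

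| First dose | Day 2 draw | t (h) | f | Ratio to 24 h |
|---|---|---|---|---|
| Day 2 | before dose | none | 0 | not applicable |
| Day 1, 08:00 | 08:00 | 24 | 0.093 | 1.0 |
| Day 1, 16:00 | 08:00 | 16 | 0.205 | 2.2 |
| Day 1, near 22:00 | 10:00 | 12 | 0.305 | 3.3 |
| Day 1, near 22:00 | 08:00 | 10 | 0.371 | 4.0 |
| Day 1, near 22:00 | 06:00 | 8 | 0.453 | 4.9 |

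With the 08:00 draw, the 10 h to 24 h ratio is 2^(14/8) = 3.4 for an 8 h half-life and 2^(14/6) = 5.0 for a 6 h half-life.

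For scale, the arms differ 3-fold in dose and exposure is dose-proportional. A 120 mg patient dosed near 22:00 (120 × 0.371 ≈ 45) would show a higher Day 2 value than a 360 mg patient dosed at 08:00 (360 × 0.093 ≈ 33).

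**Later samples, 08:00 draw, same units.**

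| First dose | Day 3 | Day 4 | Day 7 |
|---|---|---|---|
| Day 2, 08:00 | 0.093 | 0.102 | 0.102 |
| Day 1, 08:00 | 0.102 | 0.102 | 0.102 |
| Day 1, near 22:00 | 0.127 | 0.105 | 0.102 |

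For example, Day 3 after a 22:00 start is 2^(−34/7) + 2^(−24/7) = 0.034 + 0.093 = 0.127. The spread is 0.127/0.093 = 1.4-fold on Day 3 and 0.105/0.102 = 1.03-fold on Day 4.

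**PK.** On the same model, a Day 1 starter enters the Day 2 profile with 9% to 37% of the dose-1 level still present; a Day 2 starter enters with none.

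**ECG.** For a Day 1 starter the second treatment day is Day 2, so the two parts of footnote j agree. For a Day 2 starter the second treatment day is Day 3, so both cannot be met.

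**Effect of re-anchoring alone.** If the first trough is drawn before dose 2, Day 2 starters are sampled at about 24 h. Day 1 starters are still sampled at 10-24 h, because dose 2 moves to the morning slot. Re-anchoring removes the zero values but not the short first interval.

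**The case against.** Most of the case on the other side stands as a limit on size.

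- **Only one sample is badly affected.** The large spread is a worst-case pair on Day 2. A reader might infer that the whole trough series is unusable, or that timing outweighs the renal effect being sought. Halving clearance (half-life 14 h) raises the 24 h value 0.305/0.093 = 3.3-fold, which the Day 2 timing spread matches or exceeds. But the halving is itself an assumption, and the timing spread has nearly gone by Day 4.
- **The fractions may be too high.** Section 1.1.2 gives AUC/Cmax of 450/60 = 7.5 h to 500/60 = 8.3 h, whereas mono-exponential decay from peak implies 7/ln 2 = 10.1 h. Levels probably fall faster after the peak than modelled, so the 37% carry-over is likely overstated. The 10 h to 24 h ratio is less affected.
- **The ECG is not simply tied to enrolment.** A reader might infer that from Table S2. Footnote j also names the second treatment day, and the ECG is timed from a dose, so a Day 2 starter can still have an on-drug recording. The fault is a contradiction in wording.
- **PK samples are timed from a dose,** and the pre-dose sample itself measures carry-over. The pre-treatment label is the error.
- **The data allow a repair.** Administration times (SAP Listing 16.2.5.2) and trough draw times (Listing 16.2.5.4) are recorded. No pooled Day 2 analysis is specified, so harm is possible rather than certain.

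The last point does not dispose of the matter: with the trough analysis left ad hoc, nothing requires the recorded times to be used.

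**Conclusion.** The concern holds for the Day 2 samples. Followed as written, the schedule gives one trough label to undosed samples, to samples about 8-12 h after a late first dose, and to true 24 h samples. Among dosed patients the shortest-interval level is about 3.3 to 4.9 times the 24 h level (4.0 for an 08:00 draw). This rests on the 7 h half-life, mono-exponential decay and an assumed 06:00-10:00 draw. The spread falls to about 1.4-fold on Day 3 and is negligible from Day 4.

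The PK profiles mix dose-1 and dose-2 curves, the pre-treatment label is untrue for Day 1 starters, and footnote j cannot be met in full by a Day 2 starter. Neither primary outcome is affected, and the documents do not support a claim that the trough objective as a whole is compromised. This is a cheap correction worth making.

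**What to change.** 1. Define treatment day from the date of first dose. Schedule the trough draws and the PK profile by treatment day, with the profile following the same dose number in all PK participants.
2. Relabel the first PK sample as pre-dose in footnote l and Listing 16.2.5.3, and record whether the profile follows dose 1 or dose 2.
3. Reconcile footnote j (and its copy in SAP Table 1) with Protocol Sections 6.1.3 and 6.2.3.5 for both possible start days.
4. Because re-anchoring leaves a short first interval for late Day 1 starters, derive actual time since last dose and add it to Listings 16.2.5.3 and 16.2.5.4.
5. In any trough-versus-creatinine analysis, include only samples within a pre-specified window around 24 h (for example 20-28 h), or model all samples by actual time.

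The cost is wording in the protocol and SAP plus one derived variable; no extra sample is needed. With an 08:00 draw and a 20-28 h window, the first sample of anyone first dosed after about noon on Day 1 leaves the trough summary. The choice of PK dose also has a price: a dose-1 profile runs overnight in evening starters, and a dose-2 profile carries residual drug.
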